rimary objective of the proposed study is to examine the effectiveness of urally adapted digital CBT-I program compared to minimally enhanced care (mEUC) on primary outcomes: reduction in insomnia symptoms at 9 s, and 6 months post-intervention using a standard scale. Secondary mes will include quality of life, daytime sleepiness, satisfaction with care, quality, and self-reported and actigraphy-assessed wake after sleep as well as self-reported sleep onset latency at post-intervention. ratory outcomes will include actigraphy-assessed sleep duration and sleep ency.

Endpoints:	Primary Endpoint: Insomnia symptoms will be assessed at baseline, at 9 weeks (post-intervention) and at 6 months post-intervention follow-up using the ISI. Secondary Endpoints: Health-related quality of life will be assessed through the validated Short-Form 12 (SF-12), Day time sleepiness will be measured with the 8-item Epworth Sleepiness Scale at baseline, at 9-weeks, and 6- months; Satisfaction with care will be measured using a question adapted for this trial asking patients to rate the quality of professional care they have received for their symptoms of insomnia at post-intervention and 6 -months; Wake after sleep onset will be measured with self-report and actigraphy, and sleep onset latency will be measured with self-report at post-intervention. Sleep quality will be measured with the PSQI at baseline, 9 weeks, and 6- months. Sleep duration and sleep efficiency will be measured continuously and unobtrusively for 14 days at baseline and for 14-days post-intervention using the ActiWatch SpectrumPRO, an actigraphy-based device.
Study Population:	Two hundred Latina/o adult patients from primary care clinics affiliated with Columbia University Irving Medical Center and New York Presbyterian Hospital (the Ambulatory Care Network) that serves underserved communities across New York City will be enrolled into the study. Patients will be Spanish speaking or bilingual (English and Spanish) adults with moderate to severe insomnia symptoms as documented on initial eligibility screen, who are interested in receiving digital care to improve their insomnia in Spanish.
Phase or Stage: Description	Phase III trial
of Sites/Facilities Enrolling	Patients will be recruited through flyers, email, telephone, and primary care provider referrals from primary care clinics affiliated with Ambulatory Care
raiticipants.	Network (ACN) of New York Presbyterian Hospital (NYPH). The catchment areas

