1.3 SCHEDULE OF ACTIVITIES

After the cultural adaptation of Somryst developed in study 1, we will then enroll 200 patients into the RCT to compare the effectiveness of the culturally adapted digital program of CBT-I (Spanish Somryst) to minimally enhanced usual care and to determine cost-effectiveness of the intervention. Summary data from our pilot study indicate that 94 people were screened over 6 months, 52% were found eligible, and 71% completed the study. In particular, our screening in one primary care clinic over two months resulted in 22 people screened, 77% were eligible, and 71% completed the first focus group. Our pilot data indicate that we are able to screen 8 patients/month and enroll patients/month from one clinic and that an accrual rate of 12/month from multiple clinics is reasonable. The specific list of measures and schedules of activities are represented in Table 1.

Table 1. List of Measures and Schedule of Activities

	Screening/ Enrollment	Baseline	Pre-Tx	Treatment	Post-Tx (9 weeks)	6-mo Follow -Up
Procedure/Assessment/Follow -Up Windows	Virtual or in person	Virtual or in person	14 days before tx	Through Week 9 of Study	Post-Tx (9 weeks)	6-mo Post- Tx
Sociodemographic information	Х					
Insomnia Severity Index	Х	Х		Х	Х	Х
Informed Consent/Enrollment	Х					
Permission for Future Contact and Use	х					
Sleep and Depression Medicines	х				Х	Х
Sleep Disorder	х					
CAGE Assessment	Х					
Assessment for Bipolar/Psychosis/ Schizophrenia	Х					
Health Care Coverage	Х					
Assessment for Cognitive Impairment	Х					
Language Proficiency	х					
Technology Use	Х					
Referral/Contact Information	Х					
Randomization				Х		
Generalized Anxiety Disorder (GAD-7)		Х		Х	Х	Х
Epworth Sleepiness Scale (ESS)	Х	Х			Х	Х

			1	-	1
Pittsburgh Sleep Quality Index (PSQI)	Х			X	X
Quality of Life (SF-12)	Х			Х	Х
Satisfaction with Care (PACIC)	Х			Х	Х
Health Literacy	Х				
Penn State Worry Questionnaire (PSWQ)	X				
Personal Health Questionnaire Depression Scale (PHQ-8)	Х		х		
Health Care Utilization	Х			Х	Х
Medical History	Х				
Dysfunctional Attitudes and Beliefs about Sleep (DBAS-16)	Х			X	Х
Hospitalization				Х	Х
Acceptability and satisfaction with intervention				X	
Actigraphy		Х		Х	
Usability and Net promoter questionnaire				Xa	
Sleep Diary		Х		Х	
Adverse Events			Х	Х	Х

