Latina/os bear greater risk of chronic insomnia and sociocultural stressors may be important determinants of insomnia for Hispanic adults. Importantly, the prevalence of insomnia is significantly higher among Hispanics (26.5%) than non-Hispanic Whites (22.5%),⁵⁵ and this disparity is widening over time.¹⁰ Temporal analyses using the National Health Interview Survey indicate that the age-adjusted prevalence of insomnia among Hispanic/Latino adults was 16.6% in 2002 compared to 19.3% in 2012.¹⁰ Additionally, analyses of over 5,000 participants in the Hispanic Community Health Study/Study of Latinos indicates that acculturative stress, or the stress associated with integration and adaptation to the US mainland, is strongly predictive of insomnia severity (Exp(b)=1.15 (95% CI: 1.11, 1.18).⁵⁶ As such, resolution of acculturative stress may be an important intervention target in behavioral treatments for insomnia targeting Hispanics.

Chronic insomnia is undertreated in the usual primary care setting. National polls suggest that 60% of adults take some action to manage their insomnia while the remaining 40% do nothing at all or assume it will go away with time.^{11,12} Only 20% of adults seek treatment from a health care provider for their insomnia, and primary care providers serve as the first source of treatment.^{11,12,40} However, primary care providers often consider insomnia to be secondary to other psychological or physical health issues, and behavioral treatments for insomnia are rarely considered or available.^{57,58} Indeed, a recent review identified a number of primary care provider barriers to insomnia treatment including: inadequate training, time-constrained office visits, lack of discussion of sleep issues, inaccurate beliefs by both patients and providers about the importance of sleep problems, the perception among providers that

18 May 2022

insomnia treatments are ineffective and associated with significant risks, and the lack of a research base showing that treatment of insomnia improves outcomes and co-morbid conditions.¹⁸ These barriers contribute to an overall underdiagnosis and undertreatment of chronic insomnia in the primary care setting.¹⁸

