3 OBJECTIVES AND ENDPOINTS

OBJECTIVES	ENDPOINTS	JUSTIFICATION FOR ENDPOINTS	PUTATIVE MECHANISMS OF ACTION
Primary			
The primary objective of the proposed study is to examine the effectiveness of a culturally adapted digital CBT-I program compared to minimally enhanced usual care (mEUC) on reduction in insomnia symptoms at post-intervention (9 weeks), and 6 months post intervention using a standard scale.	Change in insomnia symptoms (measured with the Insomnia Severity index) from baseline to post-intervention (9 weeks) and at 6 months post- intervention will serve as the primary endpoints.	Insomnia symptoms is the primary endpoint given that the intervention targets amelioration of insomnia symptoms.	
Secondary			
Health-related quality of life	Change in mean health-related quality of life score from baseline to post-intervention (9 weeks) will serve as a secondary endpoint. Health related quality of life will be assessed through the validated Short-Form 12 (SF-12), which is a 12-item self-report	Quality of life is included as a secondary endpoint because in Aim 2_Economic analyses will compare differences in mean health-related quality of life utilities (derived from SF-12 scores).	

OBJECTIVES	ENDPOINTS	JUSTIFICATION FOR	PUTATIVE
		ENDPOINTS	MECHANISMS OF
			ACTION
	inventory that		
	generically measures		
	quality of life; it		
	yields a measure of		
	global health-related		
	weilbeing as 8		
	subscoros 82		
Daytime sleepiness	Change in mean		
Daytime sleepiness	davtime sleeniness		
	from baseline to		
	nost-intervention (9		
	weeks) follow-up will		
	serve as a secondary		
	endpoint. Sleepiness		
	will be measured		
	with the 8-item		
	Epworth Sleepiness		
	Scale, a brief,		
	validated self-report		
	scale of daytime		
	sleepiness with		
	excellent		
	psychometric		
	properties. ⁸³		
Satisfaction with care	Change in mean		
	satisfaction with		
	care from baseline		
	to post-intervention		
	(9 weeks) will serve		
	as a secondary		
	Endpoint.		
	satisfaction with		
	measured using a		
	question adapted for		
	this trial asking		
	patients to rate the		
	quality of		
	professional care		
	they have received		
	for their symptoms		
	of insomnia. ⁸⁵		
Self-reported and actigraphy	Change in mean		
assessed wake after sleep onset.	wake after sleep		
	onset from baseline		

OBJECTIVES	ENDPOINTS	IUSTIFICATION FOR	PUTATIVE
0052011120		ENDPOINTS	
	nest intervention (0		ACTION
	post-intervention (9		
	weeks) will be a		
	secondary endpoint.		

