that may exacerbate sleep difficulties. In addition to these main Cores, there are two other Cores: the Overview and Consolidation/Relapse Prevention Cores. These are critical for each user to receive in order to introduce intervention content and provide a rationale for the intervention (Overview); and integrate the educational, behavioral, and cognitive elements, promote adherence, generalize the information, help the user identify risk situations, and incorporate strategies to reduce relapse (Relapse Prevention).

Somryst relies on user-entered online Sleep Diaries to track progress and to tailor treatment recommendations (i.e., assign a "sleep restriction" window). Intervention content is enhanced through a variety of interactive features, including personalized goal-setting, graphical feedback based on inputted symptoms, animations/illustrations to enhance comprehension, quizzes to test user knowledge, patient vignettes, and video-based expert explanation.

The primary outcome, insomnia symptoms, will be assessed using the ISI at baseline, at post-intervention (9 weeks), and at a 6-month follow-up. Health-related quality of life, sleep quality, secondary outcomes, will also be assessed at the same endpoints as ISI. Daytime sleepiness, another secondary outcome will also be assessed at baseline and at the post-intervention (9 weeks), and 6-month follow-up visit. Satisfaction with care and sleep quality will be assessed at baseline and at post-intervention (9 weeks) and 6-months, and sleep duration and efficiency will be assessed 14 days prior to randomization and at post-intervention (9 -weeks).

Comparator Arm: minimally Enhanced Usual Care (mEUC)- (usual care + sleep hygiene brochure) Patients randomized to the mEUC condition will continue to receive the typical standard of care in that clinic from their primary care provider (which may include pharmacotherapy). We have labeled the condition "minimally enhanced" because patients will be provided with a sleep hygiene brochure. Minimally EUC was chosen as the comparator because it is of high clinical relevance, will allow us to determine if the adapted digital CBT-I is superior to usual care, and addresses ethical issues (i.e., identifying but not treating insomnia).⁷⁸ Patients randomized to mEUC will complete assessments on the same schedule as those randomized to the intervention arm.

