Study candidates who meet initial eligibility criteria and consent to participate will be invited to a virtual online visit where they will complete a baseline sociodemographic and psychosocial survey battery.

Secondary Outcomes:

Health-related quality of life will be assessed through the validated Short-Form 12 (SF-12), which is a 12item self-report inventory that generically measures quality of life; it yields a measure of global healthrelated wellbeing as 8 domain-specific subscores.⁸² This will be assessed at baseline and at postintervention (9 weeks) and 6-month follow-up.

Sleepiness will be measured with the 8-item Epworth Sleepiness Scale, a brief, validated self-report scale of daytime sleepiness with excellent psychometric properties.⁸³ This will be assessed at baseline and at post-intervention (9 weeks) and 6-month follow-up.

Satisfaction with care will be measured using a question adapted for this trial asking patients to rate the quality of professional care they have received for their symptoms of insomnia.⁸⁴ This will be assessed at baseline and at the post-intervention visit (9 weeks). Based on current best practices⁶⁶ of cultural adaptation of evidence-based interventions, we will also ask participants in the intervention group to

18 May 2022

rate their satisfaction with, as well as their difficulties with program content or activities after each online session.

Self-reported and actigraphy assessed wake after sleep onset and self-reported sleep onset latency will be assessed at baseline and at post-intervention for 14 days.

Sleep duration and sleep efficiency will be measured continuously and unobtrusively for 14 days following the baseline visit and post-intervention using the ActiWatch SpectrumPRO, a waterproof, lightweight, actigraphy-based device that measures physical activity continuously and can be worn for 24 hours daily. The validity of actigraphy for determining sleep duration in particular, compared with the gold standard polysomnography, is excellent.⁸⁵

Sleep quality will be measured at baseline, post-intervention, and at 6-months follow-up with The Pittsburgh Sleep Quality Index (PSQI),⁸⁶ which has excellent psychometric properties, and established validity among Spanish-speakers.⁸⁷

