Missing Data: We will use multilevel mixed models to perform intent-to-treat RM-ANOVA. There will be no missing data at baseline, because we will only randomize patients who have successfully completed the baseline assessment, and therefore all 200 patients will be included in the analyses. The software used to estimate the mixed models yields full-information maximum-likelihood parameter estimates that are robust with respect to data that are "missing at random". This will appropriately handle the possibility that attrition (or missing data) is related to either baseline level of the outcome measure, group assignment, or their interaction. However, if we discover that attrition is associated with some other characteristic (e.g., sex or age), we will use multiple imputation (chained equation approach^{104, 105}) and include the associated characteristic in the imputation model.¹⁰⁶ We will do everything possible to collect data on the reasons for dropout, who decided the participant should drop out (e.g., their PCP), and whether the dropout involves any aspect of participation in the study. Even if the patient drops out of the intervention, we will still seek to collect their key outcome information. We will compare key characteristics of participants with and without missing data. In cases where there are large differences

18 May 2022

in missing data, we will cautiously interpret our findings and will consider limitations in generalizability that might have been introduced by these differences.

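### Satisfaction with care is tested as change from baseline, with no rule for patients who have had no insomnia care to rate; a baseline-adjusted 9-week comparison would be more precise

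*Combined protocol and SAP*

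**What the plan says.** The combined document defines and schedules this endpoint in five places.

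- Section 3 makes it a change in mean satisfaction with "care from baseline" to 9 weeks.
- The synopsis (section 1.1) has patients rate the professional care "they have received for their symptoms of insomnia at post-intervention and 6 -months". Baseline is not listed.
- Section 6.1.1: "Satisfaction with care and sleep quality will be assessed at baseline and at post-intervention (9 weeks) and 6-months".
- Section 8.1: "This will be assessed at baseline and at the post-intervention visit (9 weeks"). Six months is not listed.
- Table 1 (section 1.3) appears to mark baseline, post-treatment and 6 months, although the table is broken in the text available. Its row begins "Satisfaction with Care (PACIC".

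On the instrument, section 8.1 states: "Satisfaction with care will be measured using a question adapted for this trial". The synopsis and section 3 describe the same single question, which concerns the quality of professional care for insomnia.

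On analysis, section 9.1 expects greater improvement in satisfaction under Somryst. Section 9.4.2 fits a mixed model with Group, Time (baseline included as a level) and their interaction, tests pre-versus-post interaction contrasts, and extends the analyses to the secondary endpoints. Section 9.4.3 puts the secondary endpoints under Hochberg's step-up procedure. On missing data, section 9.4.2 states: "There will be no missing data at baseline".

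**The concern.** A change score presumes that the same thing is rated twice. Here the baseline rating concerns whatever insomnia care the patient had before the trial, and the 9-week rating may concern different care. Some patients may have had no professional insomnia care by baseline. Section 2.2 says of national polls: "Only 20% of adults seek treatment from a health care provider for their insomnia". Recruitment includes flyers, email and telephone as well as provider referral (section 4.1). The data system compels an answer to most items (section 6.2.1). Without a written rule, a patient with nothing to rate either gives an answer about care that did not happen or is left blank, against the statement that baseline will be complete.

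Two things are at stake. The first is precision on an endpoint that enters a multiplicity procedure. The second is that a rule for patients without care might be chosen only after the data have been seen.

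**Working it through.** **1. The plan's own figure.** The only power statement is for the ISI (section 9.2): difference 3, SD of change 6.0, 170 patients with follow-up (85 per arm), two-sided 0.05.

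- SE = 6 × √(2/85) = 0.920, and 3/0.920 = 3.26.
- Power = Φ(3.26 − 1.96) = 90.3%. The stated 90% reproduces.
- 170/(1 − 0.15) = 200, as stated.

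No SD, effect size or correlation is given for satisfaction. What follows is in SD units, with the baseline-to-9-week correlation ρ as an assumption shown over a range.

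**2. Complete data.** With equal SDs at the two times, variances relative to an unadjusted 9-week comparison are:

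- change contrast: 2(1 − ρ)
- baseline-adjusted comparison (ANCOVA): 1 − ρ²
- ratio of the first to the second: 2(1 − ρ)/(1 − ρ²) = 2/(1 + ρ)

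The power columns assume a true difference of 0.5 SD and 85 per arm.

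| ρ | Change variance | Adjusted variance | Ratio | Power, change | Power, 9-week only | Power, adjusted |
|---|---|---|---|---|---|---|
| 0.3 | 1.40 | 0.91 | 1.54 | 78.7% | 90.3% | 92.7% |
| 0.5 | 1.00 | 0.75 | 1.33 | 90.3% | 90.3% | 96.4% |
| 0.7 | 0.60 | 0.51 | 1.18 | 98.8% | 90.3% | 99.5% |

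The ratio exceeds 1 at every ρ below 1. Against the unadjusted 9-week comparison, the change contrast is worse only when 2(1 − ρ) > 1, that is, when ρ < 0.5.

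**3. Some baseline ratings absent.** Let a share f of patients have no baseline rating, with two time points and known covariance. Likelihood estimation keeps these patients' 9-week rows. Relative variances V become:

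- planned Group × Time contrast: (1 − ρ)² + (1 − ρ²)/(1 − f)
- model with a common baseline mean: 1/[(1 − f)/(1 − ρ²) + f]

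The standard error in SD units is √(V × 2/85). At ρ = 0.5:

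| f | V, planned | SE, planned | SE, common baseline | SE, 9-week only |
|---|---|---|---|---|
| 0 | 0.25 + 0.75/1 = 1.0 | 0.153 | 0.133 | 0.153 |
| 0.4 | 0.25 + 0.75/0.6 = 1.5 | 0.188 | 0.140 | 0.153 |
| 0.8 | 0.25 + 0.75/0.2 = 4.0 | 0.307 | 0.149 | 0.153 |

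Against complete baselines, the planned contrast loses 1 − 1/1.5 = 33% of its information at f = 0.4 and 1 − 1/4 = 75% at f = 0.8.

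At ρ = 0.7 the planned contrast falls behind the unadjusted comparison once 0.09 + 0.51/(1 − f) exceeds 1. That is 1 − f below 0.51/0.91 = 0.56, or f above 0.44. The values of f are illustrations, not estimates for this trial.

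**The case against.** **Timing.** From the synopsis alone a reader might infer that no baseline rating exists. The documents do not support that: sections 6.1.1 and 8.1 and, as far as it can be read, Table 1 all plan one. The synopsis is the outlier and is terse elsewhere too, giving no times for the SF-12.

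**Share without care.** A reader might apply the 20% to the sample and conclude that only 0.20 × 200 = 40 patients could supply a change score. That figure describes adults in national polls. These are primary care patients, some referred by their providers. Only specialty behavioral treatment within 3 months is excluded, stable insomnia medication is allowed, and section 9.4.9 expects some sleep-medication users.

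**Selection.** A reader might infer that the test would be confined to earlier care-seekers. The mixed model retains patients without a baseline rating, so the cost is precision, not exclusion.

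**Precision.** The planned contrast is valid under randomization, and above ρ = 0.5 with complete baselines it beats an unadjusted 9-week comparison. No document supports a lower ρ. This stands, but it does not touch the gain from baseline adjustment, which holds at every ρ below 1.

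**Instrument.** Section 8.1 cites the PACIC development paper for its adapted question, so the Table 1 label probably names the source. It is a labelling conflict more than evidence of two instruments.

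**Follow-up.** A mEUC patient who sees nobody about insomnia may also have nothing to rate at 9 weeks, and this could differ by arm. That is right. Moving to a 9-week comparison does not by itself solve it, so the handling rule must cover follow-up as well.

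The item's response options are not shown, so a no-care option may exist. What can be said is that no scoring rule is written.

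**Conclusion.** The point holds as one about precision and specification for a single secondary endpoint. The planned contrast has 1.18 to 1.54 times the variance of a baseline-adjusted 9-week comparison for ρ from 0.7 down to 0.3. The disadvantage grows if baseline ratings are absent. This rests on an assumed ρ, equal SDs at the two times, and the reading that the section 9.4.2 model applies to this endpoint at 9 weeks. Section 9.4.2 says so explicitly only for 6 months, but section 3's change definition implies it.

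The documents do not show that the endpoint lacks a baseline, that most patients have no care to rate, or that change is always noisier than an unadjusted 9-week level. What they do show is a missing scoring rule, two schedule statements that are each incomplete, and an instrument label that differs between sections. The primary endpoint and the sample size are unaffected.

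**What to change.** - **Endpoint and analysis.** In sections 3 and 9.4.3, define the endpoint as the between-arm difference in the 9-week rating with the baseline rating as a covariate, or use the mixed model with a common baseline mean.
- **Patients with no care to rate.** Add a no-care-received response and one handling rule, fixed before outcome data are seen, for baseline and for follow-up. At baseline, an indicator beside the covariate keeps every patient in. At follow-up, receiving care comes after randomization, so the rule should keep these patients in the comparison (for example, a prespecified score with a sensitivity analysis) and report their number by arm.
- **Schedule.** Give the same time points in the synopsis, sections 3, 6.1.1 and 8.1, and Table 1. The synopsis now omits baseline and section 8.1 omits 6 months.
- **Instrument.** Use one name throughout, saying whether it is the PACIC or one question adapted from it.

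The cost is wording plus one response option, with no new visits. The result is reported as an adjusted level, not a change. With a complete baseline covariate the between-arm estimate is the same either way. For patients already interviewed without the new option, the health care utilization and sleep-medication items in Table 1 may partly show who had no care. The documents do not say whether the utilization item is specific to insomnia.
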